Specific Aim 2: To evaluate the feasibility and preliminary effectiveness of a technology-delivered FBCO intervention for L/H families in rural Nebraska using RE-AIM and i-PARIHS. We will randomly assign participants to either the intervention or an enhanced standard care group (Figure 3). Sample Size Calculation. Sample size is based on the comparison of changes in BMI z-scores achieved by participants in FC-IVR with those achieved by participants in FC-workbook condition at 6 months post randomization²⁰. A total of 46 (23 per group) parent-child dyads achieves 80% power (alpha 0.05) to detect a significant difference between SC and IVR groups conditions. To account for a 25% attrition rate at 6-month we will recruit a total of 58 (29 per group) dyads. Participant Recruitment and Baseline Assessment Procedures. [name] will coordinate the recruitment of the participants with the help of CHWs. We will recruit a total of 58 dyads (Table 1). Baseline visits will take place at local community centers using private rooms. Dyads will complete informed consent, height, weight and waist circumference assessments, as well as complete a computer-based survey. Randomization will follow a random-numbers table (families/staff unblinded). Standard-Care. Families randomized to this group will receive FC-workbook. No additional materials or intervention contact will be provided. CHWs will follow a retention protocol to ensure these individuals return to 6-month assessments. Intervention Delivery. Families randomized to this group will receive the adapted version of the intervention described above. Drs. [name] and [name] will monitor IVR completion reports and assist the student-worker and CHWs in the on-going monitoring and engagement of participants during the intervention. Measurements and Data Collection. All measures (see table at PHS section for description) will be collected prior to intervention initiation and at 6 months post baseline (Figure 3). Weight will be assessed using a digital scale calibrated for accuracy prior to each assessment period using standard weights of a known quantity (e.g., 100-pound dumbbell). Height will be measured with a stadiometer, calibrated in 0.1-cm intervals. Waist circumference will be measured with a spring-loaded cloth tape measure at the level of the iliac crest using the average of the two closest measurements. Other Measures. Children and parents will complete measures of physical activity^{98,99}, eating behaviors¹⁰⁰, beverage intake¹⁰¹, quality of life^{102,103} acculturation^{104,105}, and health literacy¹⁰⁶. Parents will also complete home environment¹⁰⁷ surveys. During the 6-month assessment parents will complete program satisfaction surveys and a short exit interview with a CHW. Feasibility will be assessed according to intervention relevant factors (RE-AIM dimensions, engagement, attendance and completion rates), cost-effectiveness, cultural

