Maintenance	
 - Characteristics of completers vs non-completers - Intention to continue the intervention - Qualitative feedback on barriers/facilitators from participants/staff and leadership using i-PARIHS constructs 	
 -Demographic and clinical data from intake surveys [SW, CHWs] -Clinical data forms at 0,12 months [CHWs] -Qualitative interviews with participants, facilitators, staff, and health authorities [[name] , PI [name]] 	

Sample Size Calculation. Sample size is based on the comparison of changes in BMI z-scores achieved by participants in FC-IVR with those achieved by participants in FC-workbook condition at 6 and 12-month post randomization. A total of 46 (23 per group)

parent-child dyads achieves 80% power (alpha 0.05) to detect a significant difference between the FC-workbook and FC-IVR conditions, based on the relative BMI z-score differences (0.05) and standard deviation related to 6-month BMI z-score reduction for FC-IVR (0.06). To account for 25% attrition rate at 12-month, we will recruit a total of 58 (29 per group) parent-child dyads.

Cost Analysis: Costs will be assessed using time tracking spreadsheets and focused primarily on Aim 2 as it relates to the intervention delivery, though costs of participant recruitment will also be tracked using material and staff time to determine dollar amounts. [name] will complete A simple cost benefit analysis by assessing intervention implementation costs at 6-month post baseline by BMI z-scores reduction categories of unchanged, ≤ 0.1 , 0.1-0.25 and ≥ 0.25 , respectively.

Qualitative Analysis. Qualitative interviews will be recorded and transcribed in English or Spanish. The PI, with assistance from Drs. [name] and [name], will construct the interview codebook, with inductive codes added iteratively by in-depth reading of transcriptions until saturation is achieved. Transcripts will be double-coded in NVivo by [name]. Inter-coder reliability using Cohens kappa (goal > 0.80) will be assessed. The research team has extensive experience conducting qualitative investigation, possesses local linguistic expertise (Drs. [name] speak Spanish), and will be aided by community partners bilingual (English-Spanish) CHW staff.

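### The cost analysis names no standard-care cost and no between-arm contrast, so as written it cannot supply the cost-effectiveness result that the feasibility assessment calls for

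*Combined protocol and SAP*

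**What the plan says.** Section 12.B (Specific Aim 2) names the factors by which feasibility is judged, as a step towards deciding on further testing. The list includes "relevant factors (RE-AIM dimensions, engagement, attendance and completion rates), cost-effectiveness, cultural" relevance and acceptability.

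Section 12.E (Cost Analysis) is the only place where a cost method is given. Costs come from time-tracking sheets and are "focused primarily on Aim 2 as it relates to the intervention delivery, though costs of participant recruitment will also be tracked". The analysis itself is "A simple cost benefit analysis by assessing intervention implementation costs at 6-month post baseline by BMI z-scores reduction categories", with four classes: unchanged, up to 0.1, 0.1 to 0.25, and 0.25 or more.

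The comparator is described in Section 12.B: "Families randomized to this group will receive FC-workbook. No additional materials or intervention contact will be provided". FC families receive the same workbook plus two group sessions and ten automated calls (Section 2, Aim 2). SC children are measured at 6 months as well: "CHWs will follow a retention protocol to ensure these individuals return to 6-month assessments".

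The effectiveness analyses do compare the arms, by a chi-square test on the proportion reducing BMI z (Section 12.B) and by a mixed model (Section 12.E). Neither comparison is linked to the cost analysis.

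**The concern.** Cost-effectiveness is a comparison: what more is spent, and what more is gained, relative to the alternative. The cost paragraph specifies neither difference. It is called a cost-benefit analysis, but it puts no monetary value on the outcome, and Section 12.B asks for something else, cost-effectiveness.

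The missing comparator matters in this design. Any effect of the workbook is common to both arms. Children enter at or above the 85th percentile, so some regression to the mean is plausible. With the cut at zero change, ordinary variation alone places many children in a reduction class. Randomisation separates these components from the effect of the sessions and calls, but only if the arms are compared.

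The classes have faults of their own. They overlap at 0.1 and 0.25, and a child whose BMI z rises has no class.

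At stake is one of the inputs to the judgement on further testing. The primary effectiveness comparison is not affected.

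**Working it through.** **Inputs.** From Section 12.E, Sample Size Calculation: between-arm difference in BMI z change 0.05; SD of 6-month reduction 0.06, stated for FC-IVR only; 23 evaluable dyads per arm; alpha 0.05; power 80%. Assumed here: normal changes, the same SD in SC, and a range for the SC mean change.

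**The plan's own figure.** n per arm = 2 × (1.960 + 0.842)² × (0.06/0.05)² = 2 × 7.85 × 1.44 = 22.6, rounded up to 23. The stated 46 in total is reproduced with a two-sided test.

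**Share reducing, SC mean change 0.**
- SC: Φ(0/0.06) = 50.0%.
- FC: Φ(0.05/0.06) = Φ(0.833) = 79.8%.
- Difference: 29.8 percentage points.
- FC reducers expected under SC anyway: 50.0/79.8 = 63%.

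By class, FC children fall 59.5% in 0 to 0.1, 20.2% in 0.1 to 0.25 and about 0% above. SC children fall 45.2%, 4.8% and about 0%. The remaining 20.2% of FC and 50.0% of SC children have no reduction; under a continuous distribution nearly all of them have an increase, for which there is no class.

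**Effect on a cost ratio.** Let C be the extra cost of an FC family over an SC family. Cost per FC reducer is C/pF. Cost per additional reducer is C/(pF − pS). Their ratio is pF/(pF − pS). Holding the 0.05 difference:

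| SC reducing | FC reducing | Difference | Ratio |
|---|---|---|---|
| 40% | Φ(−0.253 + 0.833) = 71.9% | 31.9% | 2.25 |
| 50% | Φ(0.833) = 79.8% | 29.8% | 2.7 |
| 60% | Φ(0.253 + 0.833) = 86.1% | 26.1% | 3.3 |

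Over a wider range of mean SC reduction, the ratio goes from 0.691/0.322 = 2.1 (SC worsens by 0.02) to 0.952/0.154 = 6.2 (SC improves by 0.05). If the SD were 0.12 in both arms, with SC mean change 0, it would be 0.662/0.162 = 4.1.

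**If shared cost is in the numerator.** The workbook goes to both arms. If the plan's cost per FC family is C + W, where W is the workbook cost, the ratio becomes 2.7 × C/(C + W). So 2.7 is an upper value for the 50% case. The documents give no costs, so neither W nor any dollar figure can be worked out.

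**Mean scale.** If SC improves by 0.02, the FC mean reduction is 0.07 and overstates the effect of 0.05 by 0.07/0.05 = 1.4. If SC worsens by 0.02, it is 0.03 and understates the effect.

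**Stability of a ratio.** With 23 per arm and 80% against 50%, the standard error of the difference is √[(0.80 × 0.20 + 0.50 × 0.50)/23] = 0.134. The 95% interval is 0.30 ± 0.262, or 0.038 to 0.562. Cost per additional reducer then runs from C/0.562 = 1.8C to C/0.038 = about 26C.

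**The case against.** The strongest reply is that the cost paragraph is silent rather than wrong. A reader might infer that SC children are left out of the table. The text does not say so: the classes are not restricted to FC, and Table 1 in Section 12.E reports the primary outcome by arm. That stands, and it limits the point to an unspecified comparator. It does not close the gap, because listing SC children in the table would still give no SC cost and no incremental contrast.

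A reader might also infer that the plan will publish a cost per child improved that is several times too low. The plan defines no such figure. It tabulates cost by class and does not pool the reducers, so the 2.7 describes a natural reading of the table, not a stated result.

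Nor do the documents support a general claim of bias towards adoption. The direction holds for counts of reducers in every case worked above, but on the mean scale it can reverse. Growth is a weak explanation, since BMI z is already standardised for age. The result is one item in a feasibility list without a threshold, and adoption is assessed through interviews.

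Finally, one might say that the table merely restates class counts because cost per family is nearly fixed. That is not documented. Calls completed and contact hours are tracked, and monitoring by community health workers is ongoing, so cost may vary between families.

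The objection that a full incremental analysis is too heavy for a small feasibility study stands in part. A ratio as the main result would be too unstable to inform a decision. Costs and effects shown by arm would not be heavy.

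**Conclusion.** The concern holds as a gap in specification: followed as written, Section 12.E cannot deliver the cost-effectiveness result that Section 12.B relies on. The factor of about 2.7 (2.25 to 3.3 for SC shares of 40% to 60%) is illustrative. It rests on a reading of cost per FC reducer, normal changes, an SD carried over from FC-IVR to SC, an assumed SC mean change and no shared cost in the numerator. This should be corrected before the data are analysed.

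**What to change.** In Section 12.E, Cost Analysis:
- Report by randomised arm the mean cost per family (SC workbook included, research-only costs shown separately), the mean 6-month BMI z change and the proportion reducing.
- Then report the incremental cost and the incremental effects, with bootstrap intervals that resample dyads within arm.
- Give any incremental cost-effectiveness ratio as exploratory only.
- Call it a cost-effectiveness (cost-consequence) analysis, here and in Section 12.B.
- Keep the class table as description, by arm, with non-overlapping classes and one for increases.

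No new outcome data are needed, since SC children already have 6-month BMI z. The cost is a little SC cost tracking on the existing sheets and a short bootstrap. The result will probably look less favourable, and its intervals will be wide.

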a culturally adapted technology-delivered FBCO intervention for L/H families in rural Nebraska. Applying an iterative collaborative process, we will use a mixed-methods approach to culturally adapt FC to better fit the rural L/H community profile. A Community Workgroup facilitated by our rural partner organizations in Nebraska with a high population of L/H residents and theory-and data-driven approach using structured community input adaptation process will be conducted to develop and evaluate the relevance (ecological validity and equivalence), acceptability, and usability of all the adaptations made. We hypothesize that this process will lead to a program that is relevant, acceptable, and usable by L/H families in rural communities.

Aim 2: To evaluate the feasibility and preliminary effectiveness of a technology-delivered FBCO intervention for L/H families in rural Nebraska using RE-AIM and i-PARIHS. We will randomly assign participants to either FC (n=29) or an enhanced standard-care (SC) group (n=29) and determine overall study reach, preliminary effectiveness in reducing child BMI z-scores, potential for program adoption, implementation, and sustainability through local health departments (RE-AIM outcomes). SC participants will receive a workbook. FC participants will receive a workbook, 2 in person group sessions followed by 10 IVR calls over a period of 6 months. We hypothesize that a culturally adapted FC program will lead to a higher engagement (reach, retention and completion), significant higher proportion of L/H children reducing their BMIz scores at 6 months when compared to SC group, align (social validity) with health department perceptions of i-PARIHS constructs (Innovation, context, recipient characteristics), and that FC participants will view the intervention positively (i.e. relative advantage, observability, trialability, complexity, compatibility).

3. Background and Rationale

Describe the background of the study. Include a critical evaluation of existing knowledge, and specifically identify the information gaps that the project is intended to fill.

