
relevance (aim 1 measures) and acceptability identified in exit survey/interviews to determine whether intervention is appropriate for further testing. Qualitative Analysis. Qualitative interviews and FGs will be recorded and transcribed in English or Spanish. The PI, with assistance from [name] and [name] will construct the interview codebook, with inductive codes added iteratively by in-depth reading of transcriptions until saturation is achieved. Transcripts will be double-coded in NVivo by [name], [name] and the PI. Inter-coder reliability using Cohens kappa (goal > 0.80) will be assessed. The research team has extensive experience conducting qualitative investigation^{20,22,26,51,58,62,67}, possesses local linguistic expertise (Drs. [name] and [name], speak Spanish), and will be aided by bilingual (English-Spanish) CHW staff. Statistical Analysis: The association of the intervention with the primary outcome of proportion of children reducing BMI z-scores will be tested using a chi-square test. The degree of association will be summarized using the odds ratio. If the assumptions of the chi-square test are violated, Fishers exact test will be utilized. Potential gender, and acculturation scores (external and familial language use, and social relations) differences will be explored via stratification. Comparisons between groups within gender will be done using Fishers exact test. Secondary aims outcomes include parent BMI, waist, PA, sweet beverages intake and eating behaviors, home environment changes and quality of life. The quantitative outcomes will be summarized using means and standard deviations or medians and inter-quartile ranges, as appropriate. If categorized, outcomes will be summarized using counts and percentages. Between group differences at 6-month will be capture using ANCOVA with the baseline measure as the covariate. If the ANCOVA assumptions are violated, a t-test (or if indicated, Wilcoxon's sum rank test) between group change scores (6-month baseline measure) will be used. Potential parental engagement (% of reach, retention and completion) and acculturation scores (language and media use, and social ethnic relations) differences will be explored via stratification. Comparisons between groups will be done using Fishers exact test. Significance level is 0.05.

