Effectiveness	
 -Primary outcome (BMI z-score) and secondary clinical and self-management outcomes (Table 2) by control/IVR -Comparison of outcomes in subjects who withdraw vs. complete intervention - Staff and leaderships perceptions about delivering FBCO program via IVR and group sessions 	
 -Recruitment/enrollment/subject tracking logs (including completion, dropout and loss to follow-up rates/reasons) [CHWs] -Clinical data forms and surveys at 0,6 months [SW, CHWs] -Qualitative interviews with staff and leadership [[name] , PI [name]] 	
 Selected constructs will include: Facilitation: IVR and group based sessions and workbook facilitation strategies; Innovation: adaptation to deliver strategies to L/Hs in the context of rural NE
Adoption	
 - Staff and leaderships perceptions about delivering FBCO program via IVR and group sessions 	
 -Qualitative interviews with staff and leadership [[name] , PI [name]] 	Recipients : perceptions of participants (Beneficiaries), and staff (Recipients)
Implementation	
 - IVR completion reports; group session attendance and observation reports; proportion of content delivered as intended (fidelity) - Changes made during the implementation process (adaptation) tracked by the FRAME - Number of Calls completed and contact hours - Participant satisfaction - Qualitative feedback on barriers/facilitators from L/Hs/staff using i-PARIHS constructs 	
 -IVR completion forms (IVR System) [[name]] -IVR logged call duration (IVR System) [[name]] - Participant Satisfaction survey [SW, CHWs] -Qualitative interviews with participants, staff [[name] , PI [name]] 	Context : documentation of the capacity (human and financial resources); assessment of support from the leadership at the state and local levels

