Statistical Analysis: Descriptive, parametric, and non-parametric statistical methods will be used to compare continuous and categorical variables among the intervention groups at baseline. Data will be examined for the presence of outliers, violations of normality (for those continuous variables) and missing data. Major violations of normality will be corrected with an appropriate transformation procedure or non-parametric methods . Multi-level mixed effect models will be employed to control errors of non-independence, heteroskedasticity caused by parent-child dyad heterogeneity, and potential covariates to control to detect the BMI z-score reduction differences between the two conditions. In its simplest form, the model generally can be shown as:

$$BMIZscore_{it} = \mu + \alpha_i + X_{ijt} \beta + W_i \sigma + TT_t + \theta d_i + T_t + v_{it}$$

All measures are obtained for 3 time periods: baseline, 6, and 12 months. The dependent variable is BMIZ score for participant i at time point t . The unobserved participant-level heterogeneity that is not time dependent is represented by α_i , is allowed to vary by parent-child-dyads and to be a random variable. The X_{it} are time-period-level covariates and the W_i are participant-level covariates. The model also contains treatment group indicators d_i , and

time period indicators T_t . Relative treatment effect between conditions will be captured by coefficient θ and is the variable of interest. Sensitivity analysis will be conducted to examine the robustness of the mixed effect model across different random-effect distribution specifications (e.g., normal, finite mixture of normal etc.). Additional outcomes (e.g., parent BMI, waist circumference, PA, sweet beverages intake and eating behaviors, acculturation, home environment changes and quality of life) will be analyzed using ANCOVA with the baseline measure as the covariate. If the ANCOVA assumptions are violated, a t-test (or if indicated, Wilcoxon's sum rank test) between group change scores (6 or 12 month measure and baseline measure) will be used. Significance level for all tests is 0.05. Analyses will be performed using R 3.6 (R Core Team).

F. Does this study involve the collection of blood, urine, saliva or other human biological material (HBM)?

No

DRUGS, BIOLOGIC DRUGS AND DEVICES

13. Drugs and Biologic Drugs

1. Does this research involve the use of drugs or biologics?

No

14. Devices

1. Does this research involve a medical device(s)?

No

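### The declared primary (6-month proportion reducing BMI z-score) is not the outcome the trial is powered for or models in Section 12.E, and the 12-month data that 12.E uses are not in the measures schedule

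*Combined protocol and SAP*

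**What the plan says.** **Outcome and test.** The Aim 2 hypothesis in Section 2 expects a "significant higher proportion of L/H children reducing their BMIz scores at 6 months when compared to SC group". The Statistical Analysis paragraph of Section 12.B says that the "primary outcome of proportion of children reducing BMI z-scores will be tested using a chi-square test", with Fisher's exact test as fallback, at 0.05.

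Section 12.E reads differently. The Effectiveness row of its Table 1 lists "Primary outcome (BMI z-score) and secondary clinical and self-management outcomes". Its Statistical Analysis paragraph fits a mixed-effects model to BMI z-score itself. It says of the treatment coefficient that it captures the relative treatment effect "and is the variable of interest", also at 0.05. That paragraph mentions neither the proportion nor the chi-square test, and 12.B does not mention the mixed model.

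**Sample size.** Sections 4.A.2, 12.B and 12.E all size the trial on changes in BMI z-score. Sections 4.A.2 and 12.E give a difference of 0.05 and an SD of 0.06.

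**Schedule.** In 12.B, all measures "will be collected prior to intervention initiation and at 6 months post baseline", and the measures table has columns for those two visits only. The Effectiveness row has "Clinical data forms and surveys at 0,6 months". The 12.E model text, however, says "All measures are obtained for 3 time periods: baseline, 6, and 12 months" and allows a fallback on "between group change scores (6 or 12 month measure and baseline measure". The Maintenance row of Table 1 has clinical forms at 0 and 12 months, the 12.E sample-size text compares groups at 6 and 12 months, and Section 23.A.1 pays families for visits at 0, 6 and 12 months. The same 25% attrition is dated at 6 months in 12.B and at 12 months in 4.A.2 and 12.E.

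**The concern.** Two separate things go wrong.

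First, the plan quotes 80% power for a test that it does not declare as primary. Cutting a continuous change at zero discards information, so the declared chi-square test is weaker than the comparison that set the sample size. With both analyses at 0.05 and no ranking, a non-significant chi-square could stand beside a significant model coefficient, and nothing in the plan says which is the trial's effectiveness result. The choice could then be made after the data are seen.

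Second, staff who work from 12.B and the measures table will not collect 12-month measures. The three-time-point model would shrink to two, and the 12-month clinical data in the Maintenance row would be missing, although families have been promised a paid 12-month visit. A visit that is not made cannot be recovered at the analysis stage.

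**Working it through.** **1. Reproduce the stated sample size.** Inputs from Section 12.E: difference 0.05, SD 0.06, alpha 0.05, power 80%. The plan does not state sidedness, so two-sided is assumed. For two means,

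n per group = 2 × (1.960 + 0.842)² × (0.06/0.05)² = 22.6, rounded up to 23.

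This matches the stated 23 per group (46 in total). At 23 per group the power is 80.7% by the normal formula and 78.9% by the t-test. The quoted 80% therefore belongs to a comparison of mean change.

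**2. Translate the same effect to the declared primary.** The documents give no response proportions, so these are assumptions: change is normal; the SD is 0.06 in both groups (the plan gives it for FC-IVR only); a child counts as reducing if change is below zero; and control mean change m lies between -0.05 and +0.05. Then

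- control proportion = Φ(-m/0.06)
- FC proportion = Φ((0.05 - m)/0.06)

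Power at 23 per group comes from exact enumeration of the two binomials. The n for 80% uses the pooled-variance formula for the uncorrected chi-square.

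| m | Control / FC reducing | Chi-square, uncorrected | Fisher | n per group for 80% |
|---|---|---|---|---|
| +0.05 | 20% / 50% | 57% | 45% | 40 |
| +0.025 | 34% / 66% | 62% | 50% | 37 |
| 0 | 50% / 80% | 57% | 45% | 40 |
| -0.025 | 66% / 89% | 50% | 38% | 49 |
| -0.05 | 80% / 95% | 37% | 24% | 71 |

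With a continuity correction, which the plan does not mention, power is 14% to 50%.

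**3. Apply the plan's own fallback.** 12.B moves to Fisher's test if the chi-square assumptions fail. It does not define failure, so an expected count below 5 is assumed. In the last row the expected number not reducing is 23 × (0.202 + 0.048)/2 ≈ 2.9 per group, and about 95% of tables go to Fisher. Power under this rule runs from 25% to 62% over the five rows.

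**4. How often the two analyses would part.** A t-test on change stands in for the mixed model. Under the planned effect (100,000 simulated trials per row), the t-test and the uncorrected chi-square disagree on significance in 22% to 46% of trials. Most of these have the t-test significant and the chi-square not. Under no effect (200,000 trials per scenario), at least one is significant in about 8% to 9% with the uncorrected chi-square, and about 6% to 7% with Fisher's test or the corrected chi-square.

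**5. Set the schedules side by side.**

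| Baseline and 6 months only | Relies on 12 months |
|---|---|
| 12.B Measurements and Data Collection | 12.E model and change scores |
| 12.B measures table | 12.E sample-size comparison and attrition; 4.A.2 attrition |
| 12.E Table 1, Effectiveness row | 12.E Table 1, Maintenance row; 23.A.1 paid visits |

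**The case against.** Aim 2 is feasibility and preliminary effectiveness, so low power may be acceptable. That is fair for a pilot, but the plan still hypothesises a significant difference, tests at 0.05 and quotes 80% power.

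It can also be said that 12.B is the only place that ties the primary outcome to a named test, that 12.E never calls its model primary, and that BMI z-score in Table 1 may be shorthand. The 6-month time point is indeed an inference: the 12.B sentence gives none, and the Aim 2 hypothesis does not use the word primary. Even on that reading the power mismatch remains, because it lies within 12.B itself, which sizes on mean change and tests a proportion.

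Some of the figures need care. At the 80% versus 95% end the plan's fallback would nearly always give Fisher's test, so the uncorrected 37% and the corrected 14% do not describe the analysis that would be run there; 25% to 62% is the fairer range. The disagreement and error rates use a t-test in place of a covariate-adjusted model, and the inflation under no effect is modest.

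On the schedule, the Effectiveness and Maintenance rows describe different RE-AIM dimensions and need not conflict. The Maintenance row does assign 12-month forms to the community health workers, so those data are lost only if staff follow 12.B. The real conflict is the 12.B text and table against the 12.E model, the Maintenance row and 23.A.1, and it stands.

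**Conclusion.** The concern holds and should be corrected before the analysis is fixed. The primary outcome is binary in one section and continuous in another, and the two analyses are not ranked. The stated power belongs to the continuous one. None of the five scenarios examined brings the declared test near 80% at 23 per group: 37% to 62% for the uncorrected chi-square, 24% to 50% for Fisher's test, and 25% to 62% under the plan's fallback as interpreted here. These figures rest on normal change, a common SD of 0.06 and control mean change between -0.05 and +0.05. The contradictions over outcome and visit schedule rest on the text alone and need none of these assumptions. The two dates for the 25% attrition are a smaller slip with the same cause.

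**What to change.** **Primary analysis.** State one primary analysis at 6 months, in the same words, in the Aim 2 hypothesis (Section 2), the 12.B Statistical Analysis, the Effectiveness row of Table 1 and the 12.E Statistical Analysis. The choice consistent with the stated power is continuous 6-month BMI z-score adjusted for baseline, with the proportion and any 12-month result secondary. If the proportion stays primary, restate its power or re-size for it, and label the mixed model secondary.

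**Schedule.** Take one of two routes:

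- Keep 12 months: add a 12-month column to the 12.B measures table, with at least child height and weight, and amend the 12.B data-collection text.
- Drop 12 months: remove it from the 12.E model and change scores, the 12.E sample-size comparison, the Maintenance row, the attrition statements in 4.A.2 and 12.E, and the compensation text in 23.A.1. Also check the 12-month periods in the opening summary, 4.A.1 and Section 10.

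Date the 25% attrition at one time point. While editing 4.A.2, correct its total of 56, which does not agree with 23 per group or with the 46 given elsewhere.

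**Cost.** Making the continuous outcome primary is a change of wording. Keeping 12 months needs a table column for a visit that the compensation section already funds. Dropping it also withdraws a paid visit, so participant terms change. Keeping the proportion primary means stating the lower power or recruiting more dyads: 37 to 71 completers per group for 80% with the uncorrected chi-square.
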